5.4.1.1 Hematology

Hematology assessments will include RBCs, hematocrit, Hb, platelets, and white blood cells (WBCs) with differential (basophils, eosinophils, neutrophils, monocytes, and lymphocytes). Reticulocyte count and serum erythropoietin (EPO) will also be collected.

5.4.1.2 Blood Chemistries

Blood chemistry assessments will include measurement of albumin, bicarbonate, blood urea nitrogen (BUN), calcium, chloride, creatinine, creatine kinase, glucose, lactate dehydrogenase, magnesium, phosphorus, potassium, sodium, total protein, and uric acid.

5.4.1.3 Liver Function

Liver function assessments will include measurements of serum ALT, AST, alkaline phosphatase (ALK), gamma glutamyl transferase (GGT), and bilirubin (total, direct and indirect).

5.4.1.4 Plasma Protein Samples

Blood samples for plasma protein binding assessment will be collected as indicated in the Schedules of Assessments provided in Appendix A ([Table 15-1](#) for Part A; [Table 15-2](#) for Part B).

5.4.1.5 Urinalysis

Urine will be assessed for color and appearance. Dipstick analysis for specific gravity, pH, protein, glucose, ketones, and occult blood and microscopic analysis (RBCs, WBCs, bacteria and casts) will be performed.

5.4.1.6 Electrocardiograms

12-lead ECGs should be performed after the subject has been resting in a supine or semi-recumbent position for at least 5 minutes and prior to all other non-PRO assessment. A single ECG tracing will be obtained at the indicated study visit, and must be stored at the study site. If in the opinion of the Investigator there is a clinically significant abnormality the ECG parameters should be entered into the eCRF as indicated.

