10 SAFETY ASSESSMENTS

GBT440 is not an approved drug and, as a result, the entire safety profile is not known at this time. This Phase 2 study will contribute to the understanding of the safety profile for GBT440 and for its use in IPF patients.

Safety assessments will consist of recording all AEs and SAEs, protocol-specified laboratory variables, vital signs, ECGs, and the results from other protocol-specified tests that are deemed critical to the safety evaluation of GBT440. Dedicated eCRFs will be used to collect information on specific AEs including SAEs, SUSARs, rashes and pregnancies.

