11.3 Statistical Analyses

11.3.1 Efficacy Analyses

The analysis of the primary and secondary endpoints will be summarized descriptively. Each endpoint will be summarized by dose group and overall (total subjects).

Full details of the analysis methods, including how missing data will be handled, will be provided in the SAP.

11.3.2 *Safety Analyses*

Safety and tolerability will be assessed by incidence, severity and changes from baseline of all relevant parameters including AEs, laboratory evaluations, vital signs, and ECGs.

AEs will be coded using the Medical Dictionary for Regulatory Activities (MedDRA). The number and percentage of subjects experiencing 1 or more AEs will be summarized by dose group and overall, relationship to study drug and severity according to system organ class and preferred term. Additional summaries will be provided for SAEs and events resulting in permanent discontinuation of study drug.

Laboratory parameters will be summarized using descriptive statistics and by post-dose shifts relative to baseline. Laboratory values outside normal limits will be identified in the subject listings and will include flags for high and low values.

Vital sign results and ECGs will also be summarized descriptively for each scheduled protocol time point.

11.3.3 *PK and PK/PD Analyses*

A listing of PK sample collection times as well as derived sampling time deviations will be provided. A subject listing of all concentration-time data for each treatment, and study day will be presented. PK variables will be summarized using appropriate descriptive statistics (e.g., n, mean, SD, CV%, minimum, median, and maximum, and/or geometric mean) by part, dose, and study day.

Graphical presentations of key PK parameters and concentrations will be used as appropriate. Figures of individual concentrations versus time will be presented by subject.

PK/PD analyses will be performed.

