13.2 Data Collection

The Investigator will be responsible for maintaining accurate and adequate case records (source documents) from which data will be transcribed (or if electronically captured [EDC] source data, transferred) to eCRFs designed to record data pertinent to this study. All relevant observations and data related to the study will be so recorded. This will include medical and medication history, physical examinations, a checklist of inclusion and exclusion criteria, investigational treatment administration, and a record of sample collection, clinical assessments, AEs, and final evaluation. The clinical site Clinical Research Associate (CRA) will review all eCRFs and compare data to that contained in clinic notes and subjects' source documents/medical records.

Data collected regarding each subject will be entered into the eCRF. The Investigator will be responsible for the timeliness, completeness, and accuracy of the documentation entered into the eCRFs.

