#### ***8.4.6 12-Lead Electrocardiogram***

HR (beats/min), PR interval (ms), QRS interval (ms), QT interval (ms), and QTc F interval (ms) will be summarized by the absolute value and change from baseline (Screening) at D90.

Additionally, the number and percentage of subjects with QTcF > 450 ms, >480 ms, and >500 ms at baseline and post-baseline measurement (Day 90 and Early Termination) will

be summarized by dose level and All GBT 440. The number and percentage of subjects with increase from baseline in QTcF of > 30ms and > 60 ms will also be summarized.

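### Protocol 5.4.1.6 asks for ECG parameters in the eCRF when an abnormality is judged clinically significant, but Protocol 11.3.2 and SAP 8.4.6 need them whether or not the ECG is abnormal

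*Protocol*

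**What the plan says.** **Collection.** Protocol 5.4.1.6 states: "A single ECG tracing will be obtained at the indicated study visit, and must be stored at the study site". Its next sentence is the only ECG-specific instruction on data entry: "If in the opinion of the Investigator there is a clinically significant abnormality the ECG parameters should be entered into the eCRF as indicated". It gives no instruction for an ECG without such an abnormality. No central reading or electronic transfer of ECG data is described. Both schedules (Tables 15-1 and 15-2) place the 12-lead ECG at Screening, Day 90 and Early Termination.

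**Analysis.** Protocol 11.3.2 assesses safety partly through "changes from baseline of all relevant parameters including AEs, laboratory evaluations, vital signs, and ECGs", and adds: "Vital sign results and ECGs will also be summarized descriptively for each scheduled protocol time point". In SAP 8.4.6, HR, PR, QRS, QT and QTcF "will be summarized by the absolute value and change from baseline (Screening) at D90". The same section counts subjects with QTcF above 450, 480 and 500 ms at baseline, Day 90 and Early Termination. It continues: "The number and percentage of subjects with increase from baseline in QTcF of > 30ms and > 60 ms will also be summarized". SAP 8.4 bases all safety analyses on the Safety population, and SAP 9.1 rules out imputation apart from partial dates.

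**General statements.** Protocol 10 says: "Safety assessments will consist of recording all AEs and SAEs, protocol-specified laboratory variables, vital signs, ECGs". Protocol 13.1 lists ECGs among the source documents. Protocol 13.2, after describing transcription from source documents to the eCRF, says: "All relevant observations and data related to the study will be so recorded".

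**The concern.** The analyses need unselected values. The one sentence that tells a site which ECG values to enter attaches a condition, namely the investigator's view that there is a clinically significant abnormality. If every scheduled ECG is entered anyway, that condition does nothing.

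A site could reasonably take it as the working rule. The protocol uses abnormality-driven recording elsewhere: for the physical examination, Section 5.3.3 and footnote f of the schedules ask for abnormal findings to be recorded. The eCRF instruction for SpO₂ in Section 5.5.2, by contrast, carries no such condition.

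At stake are the ECG tables. Values entered only after a judgement of abnormality would be a selected subset, so their means, changes and threshold percentages would not describe the treated subjects. Safety is the only analysis this SAP specifies, and QTcF matters enough to be an eligibility criterion. The primary objective and the adverse event endpoint do not depend on these values.

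**Working it through.** The plan gives no figure to reproduce on this point, so the check sets what each analysis needs beside what the entry sentence asks for.

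| Planned output | Values needed | Limited to abnormal ECGs? |
|---|---|---|
| Protocol 11.3.2, summary by time point | Screening, Day 90, Early Termination | No |
| SAP 8.4.6, five parameters and change | Screening and Day 90 in the same subject | No |
| SAP 8.4.6, QTcF >450, >480, >500 ms | Baseline, Day 90, Early Termination | No |
| SAP 8.4.6, QTcF increase >30, >60 ms | Screening and a post-baseline value in the same subject | No |
| Protocol 5.4.1.6, directed eCRF entry | ECGs with an abnormality judged clinically significant | Yes |

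**Example 1, baseline count.** Exclusion criterion 14 (Protocol 4.2) excludes males above 450 ms and females above 470 ms. A female with a Screening QTcF of 451 to 470 ms is therefore eligible, and she belongs in the baseline count above 450 ms. Section 5.4.1.6 directs entry of her value only if the ECG is judged clinically significant.

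**Example 2, increases.** Take a subject whose Screening ECG is unremarkable and whose Day 90 ECG is judged clinically significant. Under the conditional sentence, the Day 90 value is entered and the Screening value need not be. No change can then be calculated, and SAP 9.1 does not fill the gap. This is the kind of subject the >30 and >60 ms counts are meant to find.

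**Illustration of the literal reading.** This rests on an assumption: let q be the share of ECGs judged clinically significantly abnormal. The documents give no value, so a range of 5% to 30% is shown for a part with the planned maximum of n = 16, with ECGs independent of one another.

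- Expected values entered per visit = 16q.
- Chance of at least two values, the minimum for an SD = 1 − (1−q)^16 − 16q(1−q)^15.
- Expected Screening/Day 90 pairs = 16q² if abnormality is independent between visits. The most it can be is 16q, if the same subjects are abnormal at both.

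| q | Values per visit | Chance of ≥2 values | Pairs, independent | Pairs, at most |
|---|---|---|---|---|
| 5% | 0.8 | 19% | 0.04 | 0.8 |
| 10% | 1.6 | 49% | 0.16 | 1.6 |
| 20% | 3.2 | 86% | 0.64 | 3.2 |
| 30% | 4.8 | 97% | 1.44 | 4.8 |

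Full entry would give up to 16 values per visit and up to 16 pairs. The table shows what following the sentence literally would do. It does not estimate what happened in the trial.

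**Back-entry load.** 5 parameters × 2 ECGs (Screening plus Day 90, or Early Termination in its place) × 32 subjects = 320 values. A subject with an Early Termination ECG after Day 90 adds 5.

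**The case against.** The strongest reply is that the protocol, read as a whole, already requires full entry. Section 10 treats ECGs as recorded safety assessments. Section 13.1 makes the tracing a source document, so keeping it on site is ordinary source retention. Section 13.2 has source data transcribed to the eCRF in general terms that need not name ECGs to include them. Section 11 promises listings of all collected data. The SAP lists coagulation results without summary (8.4.4) but names five ECG parameters to be summarised, which suggests that its authors expected ECG fields in the database. The sentence in 5.4.1.6 does not contain the word *only*, and its closing words may point to eCRF instructions that are not among the documents.

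Much of this stands. A reader might infer from 5.4.1.6 that normal ECGs were left out of the database. The documents do not support that: they contain neither the eCRF nor any data, and the general sections point the other way. What the reply does not do is give the condition a purpose. A general duty and a narrower ECG-specific instruction remain side by side, and the text does not say which governs.

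Two further inferences also go too far. SAP 8.4.6 does not use every scheduled ECG in every table: Early Termination is named only for the threshold counts, and the parameter summary is for Day 90. Nor is the absence of a stated denominator in 8.4.6 a contradiction. SAP 8.4 names the population, and how subjects without a value are counted is detail that table shells and listings would normally settle.

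**Conclusion.** Wrong as written, and minor. The ECG-specific entry rule conflicts with the planned ECG analyses, and the passages must be reconciled. Confidence is high for the conflict in wording only; it does not extend to any loss of data.

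The effect on the results is zero if the eCRF captures the parameters of every scheduled ECG. If some sites entered only ECGs judged clinically significant, the QTcF and change-from-Screening tables would rest on a selected subset, of a size the documents do not reveal. Only descriptive safety tables are involved. Because the tracings are to be held at the sites, values not entered can be recovered.

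**What to change.** Check the eCRF and its completion instructions to see whether ECG parameters are captured at every scheduled ECG. Replace the conditional sentence in Protocol 5.4.1.6 with:

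*HR, PR, QRS, QT and QTcF from every scheduled ECG (Screening, Day 90, Early Termination) will be entered in the eCRF regardless of clinical significance; clinical significance is recorded separately.*

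If any values were not entered, back-enter them from the stored tracings before database lock. The SAP states that it was written before lock.

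The cost is one sentence and, at worst, about 320 data entries at full planned enrolment, plus 5 for each subject with an Early Termination ECG after Day 90. No new procedure or visit is needed, and no planned analysis changes.

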5.4.1.7 Other Clinical Laboratory Tests

For women of child-bearing potential, a pregnancy test (serum hCG) will be performed at screening, and a urine pregnancy test will be performed at Days 1, 30, 60, 90, 120 and early termination (if applicable) visits. The urine pregnancy test at Day 1 must be completed and confirmed negative before any other assessments are performed, including investigational product administration. If the urine pregnancy test is positive, the result must be confirmed with a serum pregnancy test and if positive, the subject is to be discontinued from the study.

Coagulation (Panel) including PT, PTT, and INR will be collected at screening.

5.5 Disease-Related Evaluations

5.5.1 Oxygen Titration Test (OTT)

The OTT will be used to assess the subjects' O₂ requirements at rest and with exercise, as measured by pulse oximetry and arterial blood gases (ABG). Subjects will exercise by walking along a 6MWT or equivalent course.

Refer to the separate OTT manual for complete instructions on the conduct of the OTT.

ABGs will be performed twice during the OTT:

1. Prior to the beginning of the test (i.e., prior to beginning to walk) while resting and breathing room air (i.e., with no oxygen being delivered to the subject)
2. Immediately after completion of the OTT while receiving oxygen at the flow rate being delivered at the end of the test

During the OTT, the flow of O₂ will be *titrated to maintain an SpO₂ of 89 to 92%*, using the lowest possible flow rate.

The OTT should be performed at each of the scheduled visits (Days 1, 30, 90, and 120) at approximately the same time of day (e.g., in the morning) and prior to performing the 6MWT assessment (if scheduled on the same Visit day). For safety reasons, all subjects should be clinically stable, as assessed by the study Investigator or performing technician, prior to performing the OTT.

5.5.2 Oxygen Saturation Measurement

The measurement of peripheral oxygen saturation (SpO₂) will be performed using the pulse oximeter provided by the Sponsor.

Screening and Day 1 Visit

SpO₂ measured at these visits are to determine eligibility for inclusion into the study, and will be performed at rest, breathing room air.

Prior to measuring SpO₂ breathing room air, subjects must be rested for at least 10 minutes breathing their usually prescribed flow rate of O₂. Then the subject's supplemental O₂ should be turned off to measure resting, room air SpO₂ as noted in [Section 4.1 Inclusion Criteria](#) and reproduced below.

- Resting oxygen saturation (SpO₂) between 85 and 88% for at least 30 consecutive seconds while breathing room air (refer to [Section 4.1 Inclusion Criteria](#))

Or

- Resting SpO₂ <85% for 10 consecutive seconds or, if in the opinion of the site staff, it is not safe or tolerable for the subject to continue without using their supplemental oxygen for 10 consecutive seconds whilst the SpO₂ is <85%.

Either of these 2 criteria should be met at both screening and Day 1 visits.

Vital Sign Assessments

At all scheduled vital sign assessments, SpO₂ will be measured with the subject breathing supplemental O₂, set at their usual O₂ flow rate, and after resting for at least 5 minutes. SpO₂ will be also be collected during conduct of the OTT and 6MWT (refer to the respective manuals for complete instructions).

Before recording the SpO₂ value in the eCRF, the study staff should ensure the measurement is stable, which may require continuous or repeated measurements and ensuring the subject is adequately rested.

5.5.3 Arterial Blood Gases (ABG)

Arterial blood samples will be taken at each scheduled OTT: Day 1 (baseline), Days 30, 90, and 120. Two samples will be drawn at each test:

- Prior to the beginning of the test (i.e., prior to beginning to walk) while resting and breathing room air (i.e., with no oxygen being delivered to the subject) and
- Immediately after completion of the OTT while receiving oxygen at the flow rate being delivered at the end of the test

An Allen's test should be performed prior to the resting ABG at each OTT.

The necessary equipment for performing the ABG should be prepared prior to beginning the OTT and readily available for both samples. Likewise, the necessary materials and equipment to transport the ABG samples for analysis should be readily available to ensure the integrity of the samples is not compromised.

5.5.4 6-Minute Walk Test (6MWT)

Functional exercise capacity will be evaluated at Day 1 (baseline) and Days 30, 90, and 120 using the 6MWT.

Refer to the 6MWT manual for complete instructions.

Guidelines developed by the ERS/ATS will be used for conducting the test and interpreting the results ([ATS 2002](#) and [Holland 2014](#)). Instructions for the conduct of the 6MWT will be provided in a separate manual.

The 6MWT should be performed at each scheduled visit at approximately the same time of day (e.g., in the morning) and after spirometry and DL_{CO} assessments (if scheduled on the same visit day).

As part of the 6MWT, SpO₂, heart rate, and the Borg Dyspnea Scale will be measured at the following time points: prior to starting the test, during the test, at completion of the test, and 1 minute and 2 minutes after test completion.

Refer to the 6MWT manual for complete instructions.

For safety reasons, all subjects should be clinically stable, as determined by the study Investigator or the performing technician, prior to performing the 6MWT.

5.5.5 Spirometry and Diffusing Capacity of the Lung for Carbon Monoxide (DL_{CO})

All equipment, procedures, and personnel qualifications for the assessment of lung function should be based on the recommendations of the American Thoracic Society (ATS 2003) and will be performed at each site using local equipment and procedures

Spirometry measurements will include FVC, FEV₁, DL_{CO} and other measures per the site's local practices. Post-bronchodilator assessments will not be performed.

DL_{CO} will be measured at each site by determining the diffusing/transfer capacity of the lung for carbon monoxide. DL_{CO} adjusted for Hb will also be measured.

Spirometry and DL_{CO} should be performed at screening and Day 90 at approximately the same time of day (e.g., in the morning) and before the 6MWT, if scheduled on the same visit.

Local reports from the spirometry and DL_{CO} testing will be stored on site.

5.5.6 Patient Reported Outcome (PRO) Measures

PRO assessments should be self-administered by the subject, using the paper questionnaires provided by the Sponsor, at the investigational site prior to all other non-PRO assessments and before the subject receives any disease-status information during that assessment. They will be administered as indicated in the Schedules of Assessments provided in Appendix A (Table 15-1 for Part A; Table 15-2 for Part B).

5.5.6.1 A Tool to Assess Quality of Life (ATAQ) in IPF Symptoms Questionnaire

The ATAQ-IPF Symptoms Questionnaire is an IPF-specific, self-administered questionnaire that assesses the subject's disease symptoms across three domains (physical activity, cough, and energy level) and a set of questions pertaining to O₂ use. Items are assessed using a Likert scale with a 24-hr recall period.

5.5.6.2 A Tool to Assess Quality of Life (ATAQ) in IPF Impacts Questionnaire

The ATAQ-IPF Impact Questionnaire is an IPF-specific, self-administered questionnaire that assesses how IPF affects the subjects' quality of life. Items are assessed using a Likert scale with a 1-week recall period.

5.5.6.3 St George's Respiratory Questionnaire (SGRQ)

The SGRQ is a symptom-specific 2-part, patient self-administered questionnaire that assesses shortness of breath while doing a variety of activities of daily living. This questionnaire is comprised of three domains: symptoms, activity and impact. Items are assessed on various response scales, including a 5-point Likert scale and True/False scale. The SGRQ has a recall period of 4 weeks.

5.5.6.4 Borg Dyspnea Scale

The Borg Dyspnea Scale is a 1-item assessment, self-administered by the subject as part of the 6MWT. The instrument will be used during the 6MWT to assess dyspnea from the subject's perspective. The Scale ranges from 0 (Nothing at all) to 10 (Absolute maximum/Highest possible)

5.5.6.5 End of Treatment Period Questionnaire

The End of Treatment Questionnaire is survey to evaluate the subjects' experience while on the study including symptoms, changes in oxygen saturation and use. This is a self-administered survey to be completed during the Day-90 visit. A paper version of the End of Treatment Questionnaire will be provided to the sites. Subject responses will be entered in the eCRF by the site.

5.6 Pharmacokinetic Samples

Plasma and whole blood concentrations of GBT440 will be determined using validated assays and collected pre and post drug administration (refer to [Table 5-1](#)).

Pre-dose PK samples should be obtained as soon as possible after PROs, ECG, AEs and Concomitant Medications history and vitals have been obtained and before any other assessments are performed.

Post-dose PK samples should be obtained following administration of study drug at the time points indicated in [Table 5-1](#), below. Collection of these PK samples should occur after completion of all other scheduled assessments, including spirometry and DLco, OTT, 6MWT and investigational product dosing.

Up to eleven PK samples will be collected at the following times outlined in [Table 5-1](#) (also refer to the Schedules of Assessments provided in Appendix A [[Table 15-1](#) for Part A; [Table 15-2](#) for Part B]).

Table 5-1 PK Sample Collection Schedule

	Pre-dose	15 minutes Post-dose	Between 2–4 hours Post-dose	During Study Visit
Day 1 (Visit 2)		X	X*	
Day 15 (Visit 3)	X*			
Day 30 (Visit 4)	X			
Day 60 (Visit 5)	X		X	
Day 90 (Visit 6)	X			
Day 105 (Visit 7)				X
Day 120 (Visit 8)				X

* Blood sample collection for protein binding assessment should also be collected at this time (refer to the Schedules of Assessments provided in [Appendix A \[Table 15-1 for Part A; Table 15-2 for Part B\]](#)).

Instructions for sample collection, processing and shipment are described in a separate laboratory manual.

